### Summaries

The number of days supplemental oxygen is required during screening, the treatment period and the follow-up period will be summarised categorically by treatment. The oxygen requirement for each day will be listed with the imputed oxygen status determined for the end of the treatment period.

#### **6.10.3 Exploratory Endpoints**

Biomarker data will be exploratory and the analyses data driven. Analyses and presentations of biomarker results will not form part of this SAP.

Biomarker sample collection details will be listed.

#### **6.10.4 Multiplicity**

All secondary endpoints and the supportive analyses will be considered as descriptive evidence of efficacy and will be analysed without any procedures to account for multiple comparisons.

#### **6.10.5 Country Effect**

The analyses described in Sections 6.10.1 and 6.10.2 will include country in the model as appropriate, where greater than 10 subjects are recruited per country. Summary tables will also be presented by country and overall should greater than 10 subjects be recruited per country.

#### **6.10.6 Subgroup Analyses**

The primary efficacy endpoint will be investigated using demographic and baseline value-defined subgroups as follows:

- Age ( $\leq$ median age at baseline,  $>$ median age at baseline).
- Sex (Males, Females).
- Supplemental oxygen use at baseline (Yes, No).
- CRP value at baseline ( $\leq$ median value at baseline (mg/l),  $>$ median value at baseline (mg/l)).

Each subgroup (age, sex, supplemental oxygen use and CRP) will be examined separately.

A summary table will be presented for each category of each subgroup for the primary endpoint. Analysis will be performed as described in the appropriate section for each category of the subgroup separately. Summaries and analyses will only be presented for a subgroup providing greater than 10 subjects are available for each treatment group and each category of the respective subgroup. All summaries and analyses will be presented on the FAS only.

Secondary endpoints may be explored using these subgroups and further subgroups may be also explored for all endpoints post-hoc where deemed medically appropriate following review of the data.

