## 3 SAMPLE SIZE

Sample size is based on the assumption of a standard deviation (SD) of 60 mg/L for the change in CRP from baseline to average of last two assessments during one week of treatment. With 75 patients per group and a two-sided t-test at 10% significance level, there will be an approximative 80% power to detect a true reduction of 25 mg/L in C21 treated patients compared to placebo.

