## 6 ANALYSIS PLAN

### 6.1 General

Summary statistics for continuous variables will consist of number of non-missing observations (n), mean, SD, minimum, median and maximum, unless specified otherwise.

For categorical variables the number and percentage of subjects in each category will be presented, based on the number of non-missing observations apart from disposition of subjects, protocol deviations, background and demographic characteristics, prior and concomitant medications/procedures and AEs where the percentage will be based on the number of subjects in the analysis set with a missing category presented where applicable.

The mean and median will be displayed to 1 more decimal place than the original data values and the SD will be displayed to 2 more decimal places than the original data values. The minimum and maximum will be displayed to the same number of decimal places as the original data. Percentages will be displayed to 1 decimal place; except percentages will not be presented when the count is zero and 100% for count data will be presented as an integer.

All statistical tests will be performed using a two-tailed 10% overall significance level, unless otherwise stated. The null hypothesis at all times will be that the treatments are equivalent. All comparisons between the treatments will be reported with 90% confidence intervals (CIs) for the difference.

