3.7 Rationale for Trial Design

Given the urgent need for effective medicines in COVID-19, proof of concept for C21 is sought within this randomised, double-blind, placebo-controlled phase 2 trial evaluating the safety and efficacy in subjects with COVID-19 infection who have been hospitalised and are not requiring mechanical invasive or non-invasive ventilation. The aim is to intervene early in order to prevent more serious complication such as ARDS and/or mechanical ventilation.

Approximately 150 subjects will be randomised in a 1:1 schedule to receive either standard of care + placebo or standard of care + C21 200 mg daily (100 mg *b.i.d.*[bis in die; twice daily]) for 7 days.

Rationale for the primary endpoint is supported by several very recent publications that have shown that CRP is an indicator of COVID-19 progression predicting severe disease (e.g. Li et al., 2020; Tan et al., 2020; Wang et al, 2020) and mortality (Ruan et al., 2020).

Data from the trial will guide the design of further clinical investigations of C21 in this indication.

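### Subgroup analyses are run category by category with no treatment-by-subgroup interaction, so the output never estimates whether the effect differs between categories

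*SAP*

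**What the plan says.** SAP 6.10.6 lists four two-level factors for the primary endpoint: age and baseline CRP, each split at the median, plus sex and baseline supplemental oxygen. It states that "Each subgroup (age, sex, supplemental oxygen use and CRP) will be examined separately", and then "Analysis will be performed as described in the appropriate section for each category of the subgroup separately". The only restriction is one of size: "Summaries and analyses will only be presented for a subgroup providing greater than 10 subjects are available for each treatment group" and each category, which means at least 11 per arm per category.

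The section referred to is SAP 6.10.1. Its ANCOVA has treatment and baseline CRP as terms and reports the adjusted treatment difference with SE, 90% CI and a two-sided p-value. SAP 6.1 sets the level: "All statistical tests will be performed using a two-tailed 10% overall significance level, unless otherwise stated".

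SAP 6.10.4 treats supportive analyses as descriptive and makes no multiplicity adjustment; it does not mention subgroups by name. Protocol 13.3.3.2 says that subgroups may be investigated and leaves the detail to the SAP. Neither document contains a treatment-by-subgroup term, an interaction estimate, or any rule for comparing effects between categories.

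**The concern.** A subgroup analysis asks whether the treatment effect differs between, say, younger and older subjects. The planned output does not contain that quantity. It contains pairs of separate results, each with its own p-value, and the natural but invalid reading is to contrast a significant category with a non-significant one. Each category holds only part of the sample, so its power is modest and chance alone will often put the two on opposite sides of the 10% line even when the effect is the same in both.

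What is at stake is the use made of the results. Protocol 3.7 says: "Data from the trial will guide the design of further clinical investigations of C21 in this indication". An apparent effect confined to one category could influence who is enrolled next.

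**Working it through.** **Inputs from SAP section 3.** "Sample size is based on the assumption of a standard deviation (SD) of 60 mg/L for the change in CRP"; "With 75 patients per group and a two-sided t-test at 10% significance level"; "power to detect a true reduction of 25 mg/L in C21 treated patients compared to placebo". Allocation is 1:1 (SAP section 4).

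**Assumptions.** Equal halves (37.5 per arm per category) for the median splits. The sex and oxygen splits are not given, so a range is shown. SD is 60 mg/L within every category, with no dropout and no gain from baseline adjustment unless stated.

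**1. Reproduce the plan's power.** Power = Φ(δ / (σ√(2/n)) − 1.645).
- n = 75: SE = 60 × √(2/75) = 9.80; 25/9.80 = 2.55; Φ(2.55 − 1.645) = 0.818 (noncentral t: 0.815). The stated figure of about 80% is confirmed.

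**2. Power in one half.**
- n = 37.5: SE = 60 × √(2/37.5) = 13.86; 25/13.86 = 1.804; Φ(0.159) = 0.563 (noncentral t: 0.557).

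**3. Chance that exactly one category is significant under a uniform 25 mg/L effect.** p₁(1 − p₂) + p₂(1 − p₁).
- Equal halves: 2 × 0.563 × 0.437 = 0.492 (t: 0.494). Both significant: 0.317. Neither: 0.191.
- Two equal independent halves can never exceed 50%, because 2p(1 − p) peaks at p = 0.5.

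| Split | Power, larger / smaller category | Exactly one significant |
|---|---|---|
| 50/50 | 0.563 / 0.563 | 49% |
| 60/40 | 0.630 / 0.488 | 50% |
| 75/25 | 0.714 / 0.356 | 56% |
| 85/15 (11.25 per arm, about the smallest allowed) | 0.760 / 0.256 | 63% |

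**4. Dependence on the true uniform effect (equal halves, both tails counted).** 0 mg/L: 18%; 15 mg/L: 41%; 25 mg/L: 49%; 35 mg/L: 31%; 50 mg/L: 5%. If baseline CRP had an assumed correlation of 0.5 with the outcome, the residual SD would be 60 × √(1 − 0.25) = 52.0, power per half 0.669, and the 25 mg/L figure 2 × 0.669 × 0.331 = 44%.

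**5. Four factors together.** The factors reuse the same subjects, so 1 − (1 − 0.492)⁴ = 93% is too high. A simulation (20,000 trials, four independent 50/50 factors, uniform 25 mg/L effect, t-type tests without covariates) gives the figures below. Separate runs put the any-of-four figures at 79-80% and 34-35%.

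| False signal under a uniform 25 mg/L effect | Per factor | At least one of four |
|---|---|---|
| Significant in one category only | 49% | 79% |
| Interaction test at two-sided 10% | 10% | 34% |

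**6. Power of the interaction test (equal halves).** SE of the difference between two effects = √(13.86² + 13.86²) = 19.6 mg/L.
- True difference 25 mg/L: Φ(25/19.6 − 1.645) = Φ(−0.369) = 36%.
- 80% power needs 19.6 × (1.645 + 0.842) = about 49 mg/L.

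**The case against.** The strongest reply is that the harm needs a reading that the SAP does not prescribe. The subgroups are exploratory, SAP 6.10.4 calls supportive analyses descriptive, and each category will show an estimate, SE and 90% CI. A careful reader could form an approximate contrast from those. Protocol 3.7 speaks of the trial's data as a whole and does not mention subgroups. All of this stands, and it makes the point one of interpretation. It does not supply the missing estimate: a descriptive label addresses how strongly results are claimed and how many tests are run, not whether the relevant quantity is reported.

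A reader might go further and infer that a uniform effect will usually look like a subgroup difference. For one median-split factor that is not supported: the figure is about 49% at the design effect, cannot exceed 50%, and falls when the true effect is well below or above 25 mg/L. It passes one half only for unequal splits or when all four factors are taken together.

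Nor is it fair to set about 80% for any of four factors beside 10% for one interaction test. The matched pairs are 49% against 10%, and 79-80% against 34-35%. The interaction tests would themselves raise a false flag somewhere in about a third of trials, and they have little power.

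**Conclusion.** The point holds as a limitation of the subgroup method. SAP 6.10.6 plans eight separate within-category tests and no estimate of how the effect differs. Interaction testing would cut the false signal roughly five-fold per factor (49% to 10%), and by more than half across the four (79-80% to 34-35%). The 10% rate does not depend on the size of the uniform effect, whereas the discordance rate does.

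These figures rest on SD 60 mg/L in every category, full enrolment without dropout, and independent equal splits. For unequal splits the per-factor discordance is 50-63%.

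A reader might infer that the SAP intends to declare subgroup differences from this pattern. It states no such rule. The conclusion is therefore a risk that descriptive results will be misread. The primary FAS analysis and its conclusion are not affected.

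**What to change.** Amend SAP 6.10.6 so that, for each factor, one ANCOVA is fitted on the whole FAS with treatment, baseline CRP, subgroup and treatment-by-subgroup. Include country where SAP 6.10.5 applies. Use the same scale as the primary analysis, including the log scale if the transformation branch of SAP 6.10.1 is taken, because an interaction depends on scale.

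Report the interaction estimate with its 90% CI and p-value. Show within-category estimates with 90% CIs, and state that within-category p-values are not to be compared between categories. Interactions with continuous age and baseline CRP are optional; they avoid the median cut but add two more tests.

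The cost is a few sentences of SAP text and one extra model per factor on data already collected, with no change to conduct, sample size or the primary analysis. The downside is low power: about 36% for a 25 mg/L difference between equal halves, with about 49 mg/L needed for 80%. The SAP should say that a non-significant interaction does not show that the effect is homogeneous.

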## 6.11 Safety Evaluation

A secondary endpoint is the incidence of AEs. Details regarding the evaluation of these data are given in the following section.

### 6.11.1 Adverse Events

Adverse events will be coded using the latest MedDRA dictionary version. The version used will be indicated in the data summaries and listings.

A treatment-emergent adverse event (TEAE) is defined as an AE that started on or after the start of the administration study treatment. If adverse event dates are incomplete and it is not clear whether the adverse event was treatment-emergent, it will be assumed to be treatment-emergent.

The relationship with study treatment will be entered in to the eCRF (related/not related). If the TEAE has a missing relationship it is assumed to be related to the study treatment for analysis purposes.

A summary table will present the following:

- TEAEs (events and subjects).
- Serious TEAEs (events and subjects).
- Serious study treatment-related TEAEs (events and subjects).
- TEAEs by severity (mild/moderate/severe) (events and subjects).
- TEAEs by relationship to study treatment (events and subjects).
- TEAEs leading to withdrawal from study (subjects only).
- TEAEs leading to discontinuation of study treatment (subjects only).
- Study treatment-related TEAEs leading to discontinuation of study treatment (subjects only).
- TEAEs leading to death (subjects only).

In the above summaries, if a subject experienced more than one TEAE, the subject will be counted once using the most related event for the “by relationship to study treatment” and “related to study treatment” summaries and at the worst severity for the “by severity” summary.

The following tables will be presented:

- TEAEs by SOC and PT.
- TEAEs by SOC, PT and severity.
- TEAEs by SOC, PT and relationship to study treatment.
- TEAEs leading to treatment withdrawal by SOC and PT.
- Serious TEAEs by SOC and PT.

For all of the above, SOC and PT will be presented in decreasing frequency of the total number of subjects with TEAEs.

Further details of the above five tables are given below:

1. If a subject experienced more than one TEAE, the subject will be counted once for each SOC and once for each PT.
2. If a subject experienced more than one TEAE, the subject will be counted once for each SOC and once for each PT at the worst severity.
3. If a subject experienced more than one TEAE, the subject will be counted once for each SOC and once for each PT using the most related event.

Adverse event data will be listed in full and this will also include a treatment emergent flag, the time of onset and cessation of event relative to first dosing of study treatment and duration of AE.

The listing will be repeated for serious AEs and AEs leading to treatment withdrawal.

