6.5.2 Treatment Period (Visits 2-8)

The treatment period lasts for 7 days (Visit 2-8). The procedures to be performed at each visit are specified below.

Vicore Pharma AB Version: 2.0 Trial ID: VP-C21-006 Date: 14-Aug-2020

Visit 2

Visit 2 can be scheduled as soon as the relevant screening assessments are available. Visit 2 must occur within 3 days from Visit 1 (screening).

The following procedures are performed:

- Re-evaluation of in- & exclusion criteria
- Short physical examination (including vital signs)
- Evaluation of ECG and laboratory results from Visit 1
- Assignment of randomisation number
- Concomitant medication
- Recording need of supplementary O₂
- Blood sampling for:
 - o CRP
 - Safety (haematology and biochemistry) (see Section 8.2.7)
 - o IL-6, IL-10, TNF, CA125, ferritin
 - o Biomarkers
- Urinalysis (dipstick for bilirubin, glucose, ketones, protein, specific gravity, urobilinogen and pH)
- IMP administration twice daily including diatery restrictions (see Section 5.3.2)
- Check of withdrawal criteria
- Adverse events

Visits 3-8

- Concomitant medication
- Short physical examination (including vital signs at the judgement of the Investigator)
- Recording need of supplementary O₂
- Blood sampling for
 - o CRP
 - o Safety (haematology and biochemistry) (see Section 8.2.7)
 - o IL-6, IL-10, TNF, CA125, ferritin
- Urinalysis (dipstick for bilirubin, glucose, ketones, protein, specific gravity, urobilinogen and pH)
- IMP administration twice daily including dietary restrictions (see Section 5.3.2)
- Check of withdrawal criteria
- Adverse events

In addition for Visit 8 (end-of-treatment) only:

- Pregnancy testing (urine dip-stick), if positive a blood pregnancy test must be performed to confirm positive pregnancy
- Biomarkers
- Drug accountability

Vicore Pharma AB Version: 2.0 Trial ID: VP-C21-006 Date: 14-Aug-2020

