8.2 Safety Assessments

8.2.1 Adverse Events

Adverse events will be reported from signing of informed consent until end-of-trial participation (Visit 9).

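### The TEAE definition has no clause for worsening, so an adverse event that starts before first dose and is aggravated on treatment can be absent from every AE summary table

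*SAP*

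**What the plan says.** SAP 6.11.1 fixes treatment emergence by start date alone: "A treatment-emergent adverse event (TEAE) is defined as an AE that started on or after the start of the administration study treatment". The only relaxation concerns unclear dates: "If adverse event dates are incomplete and it is not clear whether the adverse event was treatment-emergent, it will be assumed to be treatment-emergent". The protocol speaks of treatment-emergent events in 13.4.1 but does not define them.

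The AE overview in SAP 6.11.1 has nine rows and there are five tables by system organ class and preferred term (SOC/PT). All are restricted to TEAEs, for example "Serious TEAEs by SOC and PT" and "TEAEs leading to death (subjects only".

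Collection starts earlier. Protocol 8.2.1 says: "Adverse events will be reported from signing of informed consent until end-of-trial participation (Visit 9". First dose is at Visit 2, and "Visit 2 must occur within 3 days from Visit 1 (screening".

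The listings are wider than the tables. SAP 6.11.1 says "Adverse event data will be listed in full and this will also include a treatment emergent flag", and then "The listing will be repeated for serious AEs and AEs leading to treatment withdrawal". Neither listing is confined to TEAEs.

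Protocol 13.4.1 limits its AE overview to treatment-emergent events. It then plans, where appropriate, to tabulate SAEs and AEs leading to treatment withdrawal, without stating that limit. SAP 6.12 lists three changes from the protocol, and this is not among them.

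**The concern.** Adverse events are a named secondary endpoint and safety is a named objective. The population is acutely ill at consent, so some events will open before dosing, and for those the safety question is whether they get worse on C21. Under a start-date rule, an event that opens between consent and first dose cannot become treatment-emergent by worsening, whatever it turns into. If the drug aggravated such events, the AE tables, which are where the arms are compared on AEs, would not show it. Randomisation makes the omission similar in the two arms only if treatment does not affect worsening, and that is the question the tables are meant to answer.

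**Working it through.** The plan gives no figure on this point, so the check is mainly to follow one event through the planned outputs. Take a mild AE that starts the day after consent, with first dose the day after that. It becomes severe and serious on the third day of treatment and is fatal on the fifth. The site keeps it as one record.

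| Output | Depends on AE start date? | Event included? |
|---|---|---|
| Nine overview rows, SAP 6.11.1 | Yes | No |
| Five SOC/PT tables, SAP 6.11.1 | Yes | No |
| AE and SAE listings, SAP 6.11.1 | No | Yes, flagged as not treatment-emergent |
| Laboratory change and shift tables, SAP 6.11.2 | No | Through laboratory values only |
| Vital signs, SAP 6.11.4 | No | Through measured values only |
| Withdrawal reasons, SAP 6.5 | No | Yes, as a withdrawal |
| Ventilation or death, SAP 6.10.2.3 | No | Yes, as a death |

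The same death could therefore count in the ventilation analysis and be absent from the row for TEAEs leading to death. No table of all deaths or all SAEs is planned.

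**Does another rule force a new record at worsening?**
- Protocol 9.1 requires an SAE report when a concomitant illness found through screening procedures worsens or becomes serious. It gives no onset-date rule and covers only those illnesses.
- Protocol 8.2.7 makes a clinically relevant laboratory worsening since Visit 1 reportable, under conditions. It exempts an abnormality tied to an event already reported, which is the situation here.
- SAP 6.11.6 places abnormal physical findings in medical history if identified before dosing and in AEs if identified after. It does not deal with an AE that is already open.
- Protocol 9.4 follows an AE until it resolves or participation ends, and the outcome list in 9.2.3 has no category for worsening. Both are compatible with one continuing record.

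So neither document settles whether worsening produces a new start date.

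**Size.** The documents give no rate of AEs in screening and no rate of worsening. Two calculations mark out the range, both on assumptions.

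1. Share of AEs starting before first dose, if onsets were even over the observation period: s / (s + 7 + f). Here s is the 1 to 3 days from Visit 1 to Visit 2 and f is the 7 to 10 days of follow-up (protocol Table 1), with 7 treatment days.
   - Lowest: 1 / (1 + 7 + 10) = 1/18 = 5.6%.
   - Highest: 3 / (3 + 7 + 7) = 3/17 = 17.6%.

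   Only the part of this share that later worsens is affected.

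2. Expected subjects with an untabulated worsening = 150 × a × b. Here a is the proportion with an AE starting in screening and b the proportion of those that worsen on treatment. The chance of at least one is 1 − (1 − ab)^150. The values of a and b are illustrative and not from the documents.

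| a | b | Subjects of 150 | Per arm, if equal | Chance of at least one |
|---|---|---|---|---|
| 2% | 10% | 0.3 | 0.15 | 26% |
| 5% | 25% | 1.88 | 0.94 | 85% |
| 10% | 50% | 7.5 | 3.75 | nearly 100% |

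**The case against.** A reader might infer that these events are missing from every safety table. The documents do not support that. Laboratory shift tables and vital signs do not use AE start dates, and deaths count in the ventilation analyses whatever the AE onset. Likely examples are partly covered elsewhere: liver enzymes are measured at every visit except Visit 9, and worsening dyspnoea would tend to show in respiration rate, oxygen use and ventilation. This stands, and it confines the point to the AE summary tables.

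Nor are the events hidden. They are in the AE listings, which are sorted by treatment group (SAP 6.4) and can be read case by case with about 75 subjects per arm. That also stands, but a listing is not a summarised comparison of the arms.

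Illness already present at screening is largely outside the pool of pre-dose AEs, and the rules in protocol 9.1 and 8.2.7 and SAP 6.11.6 catch some worsening. This cover is real but partial, because none of these rules fixes the onset date.

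The eCRF completion instructions may say that worsening is a new record, and they are not among these documents. Silence here does not prove that no such rule exists. The SAP's definition should still not depend on an instruction it does not cite.

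Finally, it is tempting to read 6–18% as the share of AEs lost. It is not. It is the share starting before dosing under even onset, and those that never worsen are rightly not treatment-emergent.

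**Conclusion.** The gap is real and narrow. An AE with onset between consent and first dose, kept as one record, that increases in severity, becomes serious or is fatal on treatment is absent from all AE summary tables and appears among the AE outputs only in listings. This follows from the stated definition and does not depend on any rate. It does assume that the start date is known to precede dosing, since an unclear date defaults to treatment-emergent, and that the site does not open a new record.

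The number of subjects is probably small, because the pre-dose window is at most about 3 days. It cannot be computed from the documents; the illustrative range is 0.3 to 7.5 of 150.

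On the protocol, a reader might infer that the SAP contradicts 13.4.1. That goes too far: 13.4.1 states no treatment-emergent limit for the SAE and treatment-withdrawal tables, but it does not say they must include pre-dose events. What can be said is that the SAP narrows those tables and 6.12 does not record it. The change is worth making because it is cheap and concerns a named secondary endpoint. It does not put the primary analysis in doubt.

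**What to change.** Amend the definition in SAP 6.11.1 so that a TEAE is an AE that either started on or after first administration, or started before it and increased in severity or became serious (including fatal) on or after it. Add that each such event is counted once: if a site has entered the worsening as a separate record, only that record counts. Without this, the pre-dose record and the new record could both enter the event counts.

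Where the date of worsening was not captured, tabulate by arm all deaths and all SAEs present after first dose, regardless of AE onset. If the SAE and treatment-withdrawal tables stay limited to TEAEs, record that in SAP 6.12.

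A new eCRF convention is best avoided. The SAP file dates from September 2020 and covers subjects enrolled under two protocol versions, with screening planned from Q2 2020, so a change now would split recording practice within the trial.

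The cost is about one SAP sentence, a review of a few records for the date of worsening (best done before the blind is broken), and a slight rise in TEAE counts in both arms.
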